**Figure 7-1: Liver Chemistry Stopping Criteria and Increased Monitoring Algorithm**

AST= aspartate aminotransferase; ALT=alanine transaminase; INR=international normalized ratio; SAE=serious adverse event; ULN=upper limit of normal

Specific assessments and follow-up actions for potential drug-induced liver injury are provided in Appendix 6 (Section [10.6](#)).

### 7.1.2 Permanent discontinuation due to other AEs

Study participants **must be permanently discontinued from IMP** if any of the following safety-related events occur:

1. Study participant develops an illness that would interfere with his/her continued participation.
2. Study participant has a significant infective episode including but not limited to bacteremia/sepsis, infectious meningitis, septic arthritis, osteomyelitis, complicated pneumonia, or visceral abscess which may or may not result in hospitalization. This list is not intended to be all inclusive, and the investigator is expected to apply their judgement on continuing IMP based on the clinical situation (see Appendix 14; Section [10.14](#)).

---

3. Study participant has an AE of severe or serious hypersensitivity infusion-related reaction (see Appendix 15; Section 10.15) or anaphylaxis requiring corticosteroid and/or epinephrine therapy (Sampson et al, 2006).
4. Study participant has a recurrence of aseptic meningitis (Section 10.13).
5. Study participant who develops active TB, LTBI, or NTM infection during the study, regardless of initiation of TB treatment.
6. Study participant has active suicidal ideation as indicated by a positive response (Yes) to either Question 4 or Question 5 of the “Since Last Visit” version of the C-SSRS. The study participant should be referred immediately to a mental healthcare professional.
7. Study participant has new onset or recurrent neoplastic disease (except for superficial basal or squamous cell carcinoma of the skin not requiring targeted biological therapy, chemotherapy or radiation).

#### **7.1.3 Permanent discontinuation due to absence or loss of clinical benefit**

Study participants **must be permanently discontinued from IMP** if they do not experience a clinical improvement within the first 4 weeks of the Treatment Period (ie, an absence of clinical benefit) or if they experience clinical worsening (ie, a loss of clinical benefit) at any time as defined by any of the following:

1. mRS assessment
  - a. Worsening of 1 point compared with Baseline; or
  - b. Lack of improvement of a severe score (4 or 5) after 4 weeks
2. Worsening of cognitive function: A decrease of  $\geq 8$  points in the total RBANS score compared to Baseline, and per the assessment of the investigator that the study participant has worsened
3. A clinically meaningful recurrence of seizures of a previously experienced type or a new seizure type, either of those requiring a change in therapy (per the assessment of the investigator)
4. Lack of seizure improvement (per the assessment of the investigator)

If study participant permanently discontinues from IMP for any reason, investigators should contact the medical monitor, whenever possible, to discuss the withdrawal of a participant in advance. Study participants who permanently discontinue the IMP should complete the assessments outlined for the EOT/EDisc Visit and enter the 8-week SFU Period. If IMP is permanently discontinued, the requirement for, and selection of, rescue therapy will be made by the investigator.

#### **7.1.4 Temporary discontinuation of IMP**

Study participants **must be temporarily discontinued from the IMP** if any of the following events occur:

1. Study participant develops an event of hypogammaglobulinemia with a serum total IgG of  $<1\text{ g/L}$  irrespective of infection. When the IgG level reaches  $\geq 2\text{ g/L}$ , the study participant may be allowed to continue treatment with IMP (see Appendix 14; Section 10.14). In view of re-

initiating the IMP, additional samples will be collected to monitor participants' IgG levels during the period of temporary discontinuation. In order to preserve the blind (see Section 6.3.1.1 for details of mock infusions), additional participants will be selected at random and requested to provide additional samples.

2. Study participant develops an event of hypoalbuminemia with serum albumin level  $<2\text{g/dL}$ . When the serum albumin level returns to  $\geq 2.5\text{g/dL}$ , the participant may be allowed to resume treatment with IMP. In view of re-initiating the IMP, additional samples will be collected to monitor participants' serum albumin levels during the period of temporary discontinuation. In order to preserve the blind (see Section 6.3.1.1 for details of mock infusions), additional participants may be selected at random and requested to provide additional samples.
3. Study participant has a suspected drug-induced aseptic meningitis. The IMP may be restarted if clinically appropriate when signs and symptoms have resolved.

If IMP treatment is resumed, continue the next dose as previously scheduled. No "make up" dose is permitted. The participant should subsequently follow the visit schedule as described in the protocol and the eCRF should be completed accordingly.

Study participants **may be temporarily discontinued from the IMP** if any of the following events occur:

1. Study participant develops a non-serious persisting or recurrent infection with serum total IgG level between  $\geq 1$  and  $<2\text{g/L}$ . Upon resolution of infection and the IgG returning to level of  $\geq 2\text{g/L}$ , the study participant may be allowed to resume treatment with the IMP (see Appendix 14; Section 10.14).
2. Study participant may be temporarily discontinued from study medication at the discretion of the investigator in cases deemed strictly necessary for the participant's medical care. Efforts should be made to keep the length of temporary discontinuation to a minimum.

If IMP treatment is resumed, continue the next dose as previously scheduled. No "make up" dose is permitted. The participant should subsequently follow the visit schedule as described in the protocol and the eCRF should be completed accordingly.

## **7.2 Participant discontinuation/withdrawal from the study**

Participants are free to withdraw from the study at any time, without prejudice to their continued care.

A participant may withdraw from the study at any time at his/her own request, or may be withdrawn at any time at the discretion of the investigator for safety, behavioral, persistent non-manageable noncompliance, or administrative reasons.

If the participant withdraws consent for disclosure of future information, the sponsor may retain and continue to use any data collected before such a withdrawal of consent.

If a participant withdraws from the study, he/she may request destruction of any samples taken and not tested, and the investigator must document this in the site study records.

See the Schedule of Activities for data to be collected at the time of study discontinuation and follow-up and for any further evaluations that need to be completed.

### **7.2.1 Study withdrawal criteria**

Study participants **must be withdrawn from the study** if any of the following events occur:

1. Participant withdraws his/her consent.
2. The sponsor or a regulatory agency requests withdrawal of the participant.
3. Study participant becomes pregnant during the study, as confirmed by a positive serum pregnancy test.

Study participants **may be withdrawn from the study** at the discretion of the investigator, if the study participant is persistently noncompliant with the study procedures or medications and this noncompliance is not manageable in the opinion of the investigator.

Study participants who choose to withdraw from the study during the Treatment Period should complete the assessments outlined for the EOT/EDisc Visit.

Study participants who are withdrawn from the study during the Treatment Period should complete the assessments outlined for the EOT/EDisc Visit and be encouraged to enter the 8-week SFU Period.

Investigators should contact the medical monitor, whenever possible, to discuss the withdrawal of a study participant in advance.

### **7.3 Lost to follow up**

A participant will be considered lost to follow up if he or she repeatedly fails to return for scheduled visits and is unable to be contacted by the study site.

The following actions must be taken if a participant fails to return to the clinic for a required study visit:

- The site must attempt to contact the participant and reschedule the missed visit as soon as possible and counsel the participant on the importance of maintaining the assigned visit schedule and ascertain whether or not the participant wishes to and/or should continue in the study.
- Before a participant is deemed lost to follow up, the investigator or designee must make every effort to regain contact with the participant (at least 1 phone call and 1 written message to the participant), and document his/her effort (date and summary of the phone call and copy of the written message in the source documents), to complete the final evaluation. All results of these evaluations and observations, together with a narrative description of the reason(s) for removing the participant, must be recorded in the source documents. The eCRF must document the primary reason for withdrawal.

Should the participant continue to be unreachable, he/she will be considered to have withdrawn from the study with a primary reason of lost to follow up documented in the eCRF.

Study participants who are withdrawn will not be replaced.

## **8 STUDY ASSESSMENTS AND PROCEDURES**

Study procedures and their timing are summarized in the Schedule of Activities (Section 1.3). Study visits should preferably be conducted at the same time of the day throughout the study.

Some study-specific investigations may not be conducted according to the study protocol during a pandemic or other exceptional circumstance (eg, hurricanes) due to the need to implement safety measures and guidance from regulatory authorities. In such a situation, which may be accompanied by local or global containment or other measures, sites may need to prohibit access to study participants and study-related personnel. Study participants' visits to the study site may be replaced by contingency measures. These measures are primarily established to ensure the safety of study participants during the course of the study and to maintain the study participants' treatment schedules, if the investigator considers it appropriate. These measures include, but are not limited to, virtual visits or home-nursing visits replacing site visits, eg, telemedicine contacts or home-nursing visits when treatment and/or blood sampling is scheduled. The contingency measures are described in a contingency plan which will be maintained by UCB for the respective study. The contingency measures are shared with the investigator and the respective study-related personnel as soon as there are indications that it is necessary to implement any of the measures.

Immediate safety concerns should be discussed with the sponsor immediately upon occurrence or awareness to determine if the participant should continue or discontinue study treatment.

Adherence to the study design requirements, including those specified in the Schedule of Activities (Section 1.3), is essential and required for study conduct.

All Screening evaluations must be completed and reviewed to confirm that potential participants meet all eligibility criteria. Screening assessments may be performed on different days throughout the Screening Period, if required. The investigator will maintain a Screening log to record details of all participants screened and to confirm eligibility or record reasons for Screening failure, as applicable.

Procedures conducted as part of the participant's routine clinical management and obtained before signing of the ICF may be utilized for screening or Baseline purposes provided the procedures met the protocol-specified criteria and were performed within the time frame defined in the Schedule of Activities.

The study participant may have the option to have home-nursing visits as specified in Section 1.3. Home-nursing visits will be conducted by up to 2 fully trained healthcare professionals (1 unblinded for IMP preparation and 1 blinded for the other assessments) visiting the study participant at his/her home or other locations (eg, rehabilitation or day care centers, etc). Alternatively, these visits can be conducted at the site as deemed necessary by site personnel and/or study participant, or when home-nursing visits are not available. Where dosing is performed at home or at other locations, the same safety monitoring schedule will be followed as if in the clinic. Healthcare professional(s) will be present during the full duration of the visit. Home visits and visits at other locations can be conducted in case the following conditions are met:

- The study participant is willing to be dosed and monitored at home, or at an alternative location for up to 4 hours by healthcare professionals.
- The study participant has shown good acute tolerability to previous administrations of IMP (namely they must have had no moderate or severe infusion reactions, or other AEs which the investigator considers could increase the risk of home administration).

- The study participant does not require specific medical supervision based on their medical history/condition.
- The team delivering the home dose must be trained in the identification and management of infusion reactions and hypersensitivity and must have access to immediate treatments (eg, an EpiPen).
- The study participant's home or alternative location allows rapid access to emergency treatment if required (ie, the study participant must not live so remotely that a reasonable arrival time of an ambulance could not be predicted).
- The investigator is contactable to support the healthcare provider if needed.
- UCB has not requested to limit the possibility to perform home visits or visits at other locations (eg, based on IDMC recommendation).

During the home visit, a qualified site personnel will assess AEs, concomitant medications, withdrawal criteria, and the seizure diary by telephone call prior to IMP administration. During the SFU phone call, the qualified site personnel will assess AEs, concomitant medications, and evaluation of seizure diary by telephone.

The maximum amount of blood collected from each participant over the duration of the study, including any extra assessments that may be required, will not exceed 500mL. Additional blood samples may be required for repeat or unscheduled samples may be taken for safety reasons or for technical issues.

An Unscheduled Visit or assessment can be conducted at the discretion of the investigator at any time (eg, due to an AE) or to follow study participants who experience symptom worsening during the SFU Period and opt to receive rescue therapy. Assessments to be performed during an Unscheduled Visit are provided in Section 1.3.

Blood samples for PK, IgG, hematology, biochemistry, and other laboratory testing and assessments may be performed as clinically indicated at discretion of the investigator. Repeat or unscheduled samples may be taken for safety reasons or for technical issues with the samples.

## **8.1 Efficacy assessments**

Planned time points for all efficacy assessments are provided in the Schedule of Activities (Section 1.3).

### **8.1.1 Assessment of seizures**

The primary objective of the study is to assess the efficacy of rozanolixizumab as measured by seizure freedom, where seizure freedom is defined by 28 consecutive days of no seizures, maintained until the end of the Treatment Period (Week 25). Seizures will be assessed during the treatment and SFU Period and the information will be recorded using a mobile device with a pre-installed application (app) which contains a seizure diary to be completed. The presence or absence of seizures will be recorded, and if seizures were present, the number of seizures and type of seizures will be recorded. Study participants or caregivers have up to 72 hours after the end of each day to complete the seizure diary in the mobile device app. The date of data entry will be captured in the audit trail. If seizure recording is not completed within the allotted time, it will no longer be available for completion and will show as blank in the data record. An overdue

or missed entry will not impact the availability of the next day's seizure diary, as each new calendar day triggers a new diary for completion. Retrospective edits to seizure diary entries recorded in the mobile device application are not allowed after 72 hours. Daily seizure documentation is submitted electronically to the investigator. A printout of electronic records will be reviewed and discussed with the patient to ensure completeness and accuracy during the next scheduled visit. If any changes are identified during this review, they must be documented on the paper printout. Data from the printout with updates as needed are entered into the eCRF. Printed records are filed as part of the participant's source documents at site.

As a result of the discussion, the investigator will assess the seizures according to the International League Against Epilepsy codes and record the seizure types and frequency on the printout of electronic records and eCRF; he/she will also confirm the presence of AEs (if applicable). Printed records will be filed as part of the participant's source documents at site.

The recording of seizures should begin from Visit 1 (Screening). At Visit 2 (Baseline), the printout of the electronic seizure diary from Screening must be reviewed for seizure data to confirm that the study participant meets eligibility criteria before randomization.

The study participant/caregiver should be educated on how to complete the electronic seizure diary daily.

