- Faciobrachial dystonic seizures as the pathognomonic sign (Irani et al, 2011). This seizure type is unique to LGI1 AIE. Patients may also experience other types of focal seizures as well as secondarily generalized seizures.
- Cognitive symptoms including memory loss and confusion, hallucinations, rapid eye movement sleep disturbance, and psychiatric disturbance.
- Muscular symptoms which may include neuromyotonia, causing spontaneous muscular activity or twitching.
- Hyponatremia is common.
- Brain MRI showing hyperintensities in the mesial temporal lobe (Vogrig et al, 2019).

- Rarely associated with a tumor (thymoma <5%; Geis et al, 2019).
- Frequently associated with specific human leukocyte antigen haplotypes as with other IgG4-mediated diseases (Vogrig et al, 2019).
- Anti-LGI1 autoantibodies are detected in serum but often undetected in CSF (van Sonderen et al, 2016).

The array of disease features causes significant clinical burden for the patient, in particular, seizures and cognitive impairment. The majority of patients with LGI1 AIE are expected to develop seizures (~90% of patients), and all will experience at least some cognitive dysfunction over the course of their disease (van Sonderen et al, 2016). Patients with LGI1 AIE may experience various types of seizures, including FBDS, which may occur up to 100 times a day (median 40/day) with a very short duration of <15 seconds per episode (van Sonderen et al, 2016). Faciobrachial dystonic seizures are often the presenting clinical feature, with a later onset of cognitive impairment (Thompson et al, 2018). Seizures with bilateral tonic-clonic evolution usually appear in later stages of the disease at a time when cognitive impairment is also present (Vogrig et al, 2019).

Although LGI1 AIE has a clinical presentation that is distinct from other AIE, diagnosis is challenging due to initial similarity in presentation to other types of epilepsy, which can result in delayed diagnosis, a subsequent delay in appropriate treatment (de Brujin et al, 2019) and poorer outcome.

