#### **9.3.1 Primary efficacy analysis**

##### **9.3.1.1 Seizure freedom**

The primary objective of the study is the assessment of the efficacy of rozanolixizumab as measured by seizure freedom. The definition of the primary endpoint together with the description of its primary and supportive analyses are provided in [Table 9-1](#). The main intercurrent event is permanent IMP discontinuation resulting in withdrawal from the randomized Treatment Period, and entering the SFU, or the complete withdrawal from the study (see [Section 7](#)). This will include by design participants who take any rescue anti-seizure medication who will be required to be withdrawn from the randomized treatment. The other intercurrent event is a temporary IMP discontinuation. For the analyses on the RS, participants who withdraw from the study prior to receiving the IMP or who do not have any post-randomization assessment will be considered as not having met the primary endpoint.

For the purpose of deriving the primary efficacy endpoint, any intermittent missing diary seizure count recording will be imputed to non-zero in both treatment arms.

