6.1.7 Data derivation rules

6.1.7.1 Handling of dropouts or missing data

6.1.7.1.1 Efficacy data

Seizure freedom, time to seizure freedom, will be derived based on the weekly reported seizure frequency categories captured on Seizure Count CRF. Imputation methods to handle the missing data (including missing data due to intercurrent events)

In the case of all other endpoints (RBANS and mRS), the observed case method will be applied. This is also the case for any ordinal endpoints (EQ-5D-5L, CGI-S). No imputation of data will be applied.

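### The 72-hour diary lock does not bind the analysed seizure data, and the SAP holds two different rules for a missing day

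*Protocol*

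**What the plan says.** Protocol 8.1.1 sets the entry window: "Study participants or caregivers have up to 72 hours after the end of each day to complete the seizure diary". A day not entered in that time is closed: "it will no longer be available for completion and will show as blank in the data record". The ban on later changes is limited to the app: "Retrospective edits to seizure diary entries recorded in the mobile device application are not allowed after 72 hours".

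The same section adds a second route into the data: "A printout of electronic records will be reviewed and discussed with the patient to ensure completeness and accuracy during the next scheduled visit". Changes are written on the paper copy, and then "Data from the printout with updates as needed are entered into the eCRF". Protocol 10.1.7 gives the app record the same role, as the basis for a discussion after which the investigator reports seizure information in the eCRF.

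On the analysis side, SAP 6.1.7.1.1 derives seizure freedom from weekly reported frequency categories "captured on Seizure Count CRF". For a missing day, Protocol 9.3.1.1 states that "any intermittent missing diary seizure count recording will be imputed to non-zero in both treatment arms", and SAP 5.3.1 also treats such a day as non-zero. SAP Table 5-1, to which Table 5-2 refers for the primary estimand's missing-data strategy, instead fills a missing daily count with the average of the observed days in that period.

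**The concern.** A lock and a conservative missing-day rule normally work together: what was not recorded in time stays missing, and missing counts against success. Here the two are separated. The lock applies to the app and the analysis uses the CRF. Between them is a review whose purpose includes completeness, with no exclusion for locked days, no limit on the age of an updated day, no requirement for a source made at the time, and no flag for analysis.

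Two sites could both follow the protocol and score the same participant differently, one leaving the blank and the other entering zero. The endpoint needs 28 consecutive seizure-free days held to Week 25, so one day can decide responder status. The reader of the results could not tell which responders depend on days entered after the lock.

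**Working it through.** **The plan's own figure.** This point is about data flow and has no stated figure, but the design power is used below, so it is checked first. Inputs from Protocol 9.8 and Table 9-6: N=60 (n=30 per arm), two-sided 5%, 40% v 80% seizure-free, continuity-corrected test.

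Power = Φ{[|p1−p2| − 1/n − 1.96√(2p̄(1−p̄)/n)] / √[(p1(1−p1)+p2(1−p2))/n]}

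= Φ{[0.400 − 0.033 − 0.248] / 0.1155} = Φ(1.03) = 84.8%, against 84.5% stated. The design figure is not in dispute.

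**One blank among otherwise zero days in the final 28.**

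| Missing-day rule | Left blank | Entered later as zero |
|---|---|---|
| Protocol 9.3.1.1, SAP 5.3.1 (non-zero) | Failure | Success |
| SAP Table 5-1 (period average) | Average of zeros is zero: success | Success |

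The step from failure to success therefore rests on the first rule. The SAP contains both.

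**How many participants could be affected.** The blank-day rate q is not in the documents, so it is an assumption, with independent days and the same q in both arms. For a participant truly seizure-free over the last 28 days, P(at least one blank) = 1 − (1−q)^28.

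| q | (1−q)^28 | P(at least one blank) |
|---|---|---|
| 0.2% | 0.9455 | 5.45% |
| 1% | 0.7547 | 24.5% |
| 2% | 0.568 | 43.2% |
| 5% | 0.238 | 76.2% |

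**Effect on what will be reported.** SAP 3 gives 12 participants, and SAP 5.3.2 keeps the odds ratio with its 95% CI. Illustration, assuming 6 per arm and placebo 2/6:

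- Rozanolixizumab 3/6: OR = (3×4)/(2×3) = 2.0. SE of log OR = √(1/3+1/3+1/2+1/4) = 1.19. 95% CI 0.19 to 20.6.
- Rozanolixizumab 4/6: OR = (4×4)/(2×2) = 4.0. SE = √(1/4+1/2+1/2+1/4) = 1.22. 95% CI 0.36 to 44.1.

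One reclassified participant doubles the point estimate, inside intervals too wide to support a conclusion either way.

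**What a strict lock costs.** If every blank stays as non-zero, true rates of 80% v 40% are observed as 80% and 40% multiplied by (1−q)^28. At q=1% that is 60.4% v 30.2%, and at q=2% it is 45.4% v 22.7%. The power formula above then gives 55.4% and 34.9% at N=60. If every blank is entered as zero, the rates return to 80% v 40%.

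**The case against.** Several points on the other side are sound.

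- **Filling blanks is permitted, not stated.** No sentence tells a site to fill a locked day. Section 8.1.1 gives another reason for updates, since the investigator classifies seizures and records type and frequency on the printout. Changes are documented on a filed source record, app entry dates are in the audit trail, and Protocol 10.1.6 provides for source verification and reasons for eCRF changes. The Amendment 3 entry in the amendment history (superseded text, used only as history) suggests that locking the app while allowing edits on paper was deliberate.
- **Recall is short and may be assisted.** Inclusion criterion 9a requires a reliable caregiver, who may complete the diary and join the discussion. Doses are 7 ± 2 days apart and the diary is also assessed by telephone at home visits. A locked day is already more than 72 hours old, but usually no more than about 9 days.
- **Cognition.** A reader might infer from Section 2.1, "all will experience at least some cognitive dysfunction over the course of their disease", that every participant's recall is unreliable. That sentence describes the disease over its course. Section 4.2 allows participants with RBANS above 85, whom it regards as cognitively normal.
- **A strict lock has its own error.** The shares above are of truly seizure-free participants, for whom zero is the correct value. A rule that always keeps the blank would fail them. The documents give no basis for estimating how many late zeros would be false.
- **The consequence is limited.** There are 12 participants and no test, and rewriting 8.1.1 cannot change how data already collected were entered.

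These points remove the case for making the locked diary the only primary source. They do not supply a rule for locked blanks, a day-level data source, or a way to see which days were changed.

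**Conclusion.** The point holds as a gap in the data rules. The lock does not reach the CRF data from which seizure freedom is derived. Under the non-zero rule, the same blank can give either result. The SAP's two missing-day rules disagree, and its stated source, weekly categories, is not clearly at the day level that the endpoint needs.

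The size is conditional: 5% to 76% of truly seizure-free participants could have an outcome that turns on a blank day, for assumed blank rates of 0.2% to 5% with independent days. The odds-ratio example also assumes 6 per arm.

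Two stronger readings are not supported. A reader might infer that late entries favour rozanolixizumab, but the trial is double-blind, both arms follow the same procedure, and nothing shows a difference by arm. A reader might also infer that a significance result is at risk, but SAP 2 and 5.3.2 have dropped hypothesis testing. What is affected is the reported odds ratio and the listings.

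**What to change.** - In SAP 5.3.1 and 6.1.7.1.1, name the seizure data source at day level and state one missing-day rule. Remove or correct the primary-endpoint entry in Table 5-1 to match.
- In the daily seizure listing, flag every eCRF day that was blank or different in the app record at the 72-hour lock.
- Report the primary-endpoint 2×2 table and odds ratio both ways: with eCRF-updated days, and with days blank at lock kept as missing (non-zero).
- Fix which version is primary before unblinding.

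The cost is SAP wording, one extra summary, and a comparison of app and eCRF records for 12 participants, using an audit trail and filed printouts that the protocol already requires. The downside is that the locked-diary version will count some truly seizure-free participants as failures; showing both versions makes that visible.
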